8. RESEARCH QUESTION AND OBJECTIVES

Research question: What is the real-world data on antidepressant therapy that can be found in the nationwide claims database in Korea?

Primary objectives:

- Explore baseline characteristics and drug utilization patterns of 11 commonly used antidepressant therapy during 90 days of acute treatment phase
 - o Top 11 commonly used antidepressants according to local market data are as follows:
 - Escitalopram, paroxetine, fluoxetine, mirtazapine, duloxetine, sertraline, venlafaxine, tianeptine, vortioxetine, desvenlafaxine, bupropion
 - o Proportion of antidepressants prescribed by sex, age (≤ 20 , 21-64, ≥ 65), sex and age combined
 - o Initial doses used, average daily doses of each antidepressants
 - o Average length of treatment with index medication before therapy change occurs (switching, combination, augmentation, discontinuation)

- Adherence and persistence measured by medication possession ratio during first 90 days of treatment period
- Explore drug utilization patterns such as therapy changes, medication compliance and recurrence relationship, and risk of adverse outcomes during maintenance phase
 - The choice of antidepressant, average length of new treatment maintenance, average number of co-administered medications (e.g., atypical antipsychotics, mood stabilizer, thyroid hormone, psychostimulant) when following changes occur from initial monotherapy:
 - Switching
 - Combination
 - Augmentation
 - Medication compliance and recurrence
 - Compliance measured as adherence and persistence
 - Recurrence
 - Relationship between recurrence and compliance
 - Risk of adverse outcomes measurement between individual ADs that are well known to be treatment-related (e.g., hyponatremia, GI bleeding, fractures, falls, risk of intracranial hemorrhage, attempted suicide/self-harm, myocardial infarction, epilepsy/seizures, stroke/transient ischemic stroke)

Secondary objectives:

1. Choice of antidepressants and drug utilization patterns in patients with various comorbidities
 - Psychiatric comorbidities
 - Mild cognitive impairment (MCI)
2. The relationship of non-pharmacologic treatment and discontinuation, medication compliance
 - Non-pharmacologic treatments may include: cognitive behavioral therapy (CBT),

frequency of physician visit during acute and maintenance phase of treatment

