Adverse outcomes	Primary outcome	HIRA Database	
The following known treatment related outcomes will be operationally defined by KCD-7 diagnosis codes and/or NHI procedure codes in medical claims
 
 - GI bleeding I850, I883, K2211, K226, K228, K250, K252, K254, K256, K260, K262, K264, K266, K270, K272, K274, K276, K280, K282, K284, K286, K290, K3181, K5521, K625, K920, K921, K922 - Fractures S02, S12, S22, S32, S42, S52, S62, S72, S82, S92, T02, T08, T10, T12, T14.2 - Falls W00-W19 - Intracranial hemorrhage I60, I61, I62, I690, I691, I692, S064, S065, S066, S068 - Suicide attempt, self-harm T40 Poisoning by narcotics and psychodysleptics [hallucinogens] T41 Poisoning by anaesthetics and therapeutic gases T42 Poisoning by antiepileptic, sedative-hypnotic and antiparkinsonism drugs T43 Poisoning by psychotropic drugs, not elsewhere classified T54 Toxic effect of corrosive substances T60 Toxic effect of pesticides X60-X84 intentional self-harm - Myocardial infarction I21.9, I21.4, I21.0, I21.1, I21.2, I21.3, I22.0A, I22.0B, I22.0C, I22.8A,

PFIZER CONFIDENTIAL

			
I22.8B, I22.8C, I22.8D, I22.8E, I22.8F, I22.8G, I22.8H, I22.8I, I22.8, I22.9, I22.1A, I22.1B, I22.1C
 
 - Epilepsy/seizures G40.XX - Stroke 
 - Transient ischemic attack G459, I63, I693 - Hemorrhagic stroke I60, I61, I62, I690, I691, I692 - Ischemic stroke I63 
[NOTE] Hospitalization and CT or MRI codes such as brain CT or MRI procedure code for ischemic stroke and hemorrhagic stroke, or any CT or MRI for systemic embolism are also required for identification.
 
 * Brain CT HA441, HA451, HA461, HA471, HA851 * Brain MRI HE101, HE102, HE135, HE201, HE202, HE235, HE301, HE302, HE401, HE402, HE501, HE502, HE535 * Any CT or MRI or CT HA401-HA416, HA424, HA425, HA434, HA435, HA443-HA449, HA453, HA456-HA459, HA463-HA469, HA473-HA479, HA496, HA497, HA801, HA805, HA809, HA813, HA834, HA835, HA853, HA856, HA857-HA859, S852 * MRI HE103-HE142, HE203-HE234, HE236-HE241, HE303-HE334, HE403-HE434, HE430-HE434, HE503-HE534, HE536-HE541, HF101, HF102, HF104-HF107, HF201, HF202, HF305, HF306 
 - Hyponatremia 
 - will be identified by
--	--	--	---

			prescription codes for vasopressin receptor antagonists such as tolvaptan (drug code=616501ATB)

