9.7. Data analysis

The proportions and drug utilization patterns comparisons of 11 study drugs will use all the patients satisfying inclusion and exclusion criteria (raw data). Adherence, persistence, discontinuation, recurrence, and adverse outcomes comparison of 11 study drugs will use both raw data and matched data where patients will be matched on demographic and clinical characteristics. All outcome variables will be summarized *descriptively* through the tabular and graphical display of mean values, medians, ranges and standard deviations of continuous variables of interest and frequency distributions of categorical variables. Safety outcomes of treatments will be estimated from time-to-event models. The 95% confidence intervals for the estimates will be calculated and $p < 0.05$ will be considered significant. All analyses will be carried out using SAS version 9.4 which is installed on HIRA server. Analysis and reporting will be compliant with Strengthening the Reporting of Observational Studies in Epidemiology (STROBE) recommendations.

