5.2 SAFETY ENDPOINTS

Adverse outcomes are primary endpoints in this study and they include the following categories defined by KCD-7 diagnosis codes and/or NHI procedure codes appearing in medical claims data after the index date.

- GI bleeding
I850, I983, K2211, K226, K228, K250, K252, K254, K256, K260, K262, K264, K266, K270, K272, K274, K276, K280, K282, K284, K286, K290, K3181, K5521, K625, K920, K921, K922
- Fractures
S02, S12, S22, S32, S42, S52, S62, S72, S82, S92, T02, T08, T10, T12, T14.2
- Falls
W00-W19
- Intracranial hemorrhage
I60, I61, I62, I690, I691, I692, S064, S065, S066, S068
- Suicide attempt, self-harm
T40 Poisoning by narcotics and psychodysleptics [hallucinogens]
T41 Poisoning by anaesthetics and therapeutic gases
T42 Poisoning by antiepileptic, sedative-hypnotic and antiparkinsonism drugs
T43 Poisoning by psychotropic drugs, not elsewhere classified
T54 Toxic effect of corrosive substances
T60 Toxic effect of pesticides
X60-X84 intentional self-harm
- Myocardial infarction
I21.9, I21.4, I21.0, I21.1, I21.2, I21.3, I22.0A, I22.0B, I22.0C, I22.8A, I22.8B, I22.8C, I22.8D, I22.8E, I22.8F, I22.8G, I22.8H, I22.8I, I22.8, I22.9, I22.1A, I22.1B, I22.1C
- Epilepsy/seizures
G40.XX
- Stroke
 - Transient ischemic attack
G459, I63, I693
 - Hemorrhagic stroke
I60, I61, I62, I690, I691, I692
 - Ischemic stroke
I63

[NOTE] Hospitalization and CT or MRI codes such as brain CT or MRI procedure code for ischemic stroke and hemorrhagic stroke, or any CT or MRI for systemic embolism are also required for identification.

- Brain CT
HA441, HA451, HA461, HA471, HA851
- Brain MRI
HE101, HE102, HE135, HE201, HE202, HE235, HE301, HE302, HE401, HE402, HE501, HE502, HE535
- Any CT or MRI or CT

HA401-HA416, HA424, HA425, HA434, HA435, HA443-HA449, HA453, HA456-HA459, HA463-HA469, HA473-HA479, HA496, HA497, HA801, HA805, HA809, HA813, HA834, HA835, HA853, HA856, HA857-HA859, S852

- MRI
HE103-HE142, HE203-HE234, HE236-HE241, HE303-HE334, HE403-HE434, HE430-HE434, HE503-HE534, HE536-HE541, HF101, HF102, HF104-HF107, HF201, HF202, HF305, HF306
- Hyponatremia
Will be identified by prescription codes for vasopressin receptor antagonists such as tolvaptan (drug code=616501ATB)

CC
I

[figure not shown]

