7 STATISTICAL METHODOLOGY AND STATISTICAL ANALYSES

7.1 STATISTICAL METHODS

Means, medians, and standard deviations will be provided for continuous variables when performing descriptive analysis of continuous data. Numbers and percentages will be provided for dichotomous and polychotomous variables when performing descriptive analysis of categorical data. Bivariate comparisons of baseline characteristics and outcomes measures will be provided. Appropriate tests (e.g., t-test, chi-square test) will be used based on the distribution of the measure. The cumulative incidence rate for clinical outcomes (major bleeding event, and stroke) will be calculated. The incidence rate will be calculated as the number of patients who experience the event divided by the observed time at risk. An unadjusted Kaplan Meier curve will be drawn to illustrate time-to-event.

PFIZER CONFIDENTIAL

[figure not shown]
The propensity score matching (PSM) technique and the propensity score weighting technique will be used to control for confounders when comparing the antidepressants. After PSM, no significant differences are expected among all pre-index measures between the antidepressant cohorts except for clinical indication differences. Also covariates in Table 3 will be included in multivariate logistic regression framework for each antidepressant choice (binary variable of 1 for choice and 0 for no choice). Covariates will include variables such as age, geographic region, CCI score, and comorbidities. Non-pharmacologic treatments will be used as a covariate if dependent variable is adherence, persistence, or discontinuation since a previous study reported accompanying number of non-pharmacologic treatments significantly increase adherence of antidepressants (Ahn J et al., 2011). The final lists of variables to be used in the model will be discussed and determined during analysis development, after reviewing the pre-matched descriptive tables and post-matched pre-index measures. All data analysis will be executed using statistical software SAS version 9.4 or later.

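### The transient ischemic attack (TIA) code list contains the plan's whole code definition of ischemic stroke (I63), so the two sub-outcomes cannot be read as separate results

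*Protocol*

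**What the plan says.** Protocol 9.3, Table 3, Adverse outcomes, has a Stroke block with three sub-items:

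- "Transient ischemic attack G459, I63, I693"
- "Hemorrhagic stroke I60, I61, I62, I690, I691, I692"
- "Ischemic stroke I63"

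A note below the block makes further codes a condition of identification: "Hospitalization and CT or MRI codes such as brain CT or MRI procedure code for ischemic stroke and hemorrhagic stroke", and any CT or MRI for systemic embolism. The note does not mention TIA. SAP 5.2 and SAP Table 3 carry the same three lists and the same note.

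On the role of these outcomes, SAP 5.2 states: "Adverse outcomes are primary endpoints in this study". The objective in Protocol section 8, a comparison between individual antidepressants, names them in one run: "myocardial infarction, epilepsy/seizures, stroke/transient ischemic stroke". Protocol 9.7 adds: "Safety outcomes of treatments will be estimated from time-to-event models", with 95% confidence intervals and a 0.05 significance level. SAP 7.1 says: "The cumulative incidence rate for clinical outcomes (major bleeding event, and stroke) will be calculated"; TIA is not named there.

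Neither document gives a hierarchy among the three sub-items, a rule that keeps I63 out of TIA, a reason for listing it there, or any frequency of G459, I63 or I693.

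**The concern.** TIA and ischemic stroke stand side by side as sub-items of a primary safety outcome, yet the first contains all of the second. As written, the TIA count for any drug cannot be lower than its ischemic stroke count.

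If the sub-items are reported separately, two things follow. A drug difference confined to TIA is diluted by ischemic strokes. A drug difference confined to ischemic stroke shows up under both labels and can look like two findings.

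The second issue is case confirmation. The plan asks for hospitalization and brain imaging before an I63 claim counts as ischemic stroke. If that condition does not extend to the TIA line, an I63 claim that fails it is still a case, under the TIA label.

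**Working it through.** The plan states no event count, rate or power figure on this point, so there is nothing to reproduce. The check is a comparison of code sets, followed by a sensitivity calculation on assumed ratios.

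**Step 1: code sets** (Protocol Table 3; identical in SAP 5.2 and SAP Table 3)

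- TIA = {G459, I63, I693}
- Ischemic stroke = {I63}
- Hemorrhagic stroke = {I60, I61, I62, I690, I691, I692}

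Ischemic stroke lies wholly inside TIA, and the shared code is I63. TIA and hemorrhagic stroke share no code. The containment holds however the imaging note is read: a confirmed I63 case carries I63, hospitalization and imaging, so it meets the TIA line with or without that condition.

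**Step 2: the composite**

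The union of the three lists is {G459, I60, I61, I62, I63, I690, I691, I692, I693}, whether or not I63 is in the TIA line. A patient counted once at the first event is not counted twice. What can change is the condition under which I63 counts: confirmed if it enters only as ischemic stroke, possibly unconfirmed if it also enters as TIA.

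**Step 3: size, if TIA is reported separately**

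Let r be the number of reported TIA cases who enter through I63, divided by the number who enter through G459, in the reference drug group. The documents do not give r, so 0.25, 1, 2 and 4 are assumed. I693 and patients with both codes are ignored.

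- Share of I63 among TIA cases: s = r / (1 + r)
- Reported TIA ratio: (1 − s) × (true TIA ratio) + s × (true ischemic stroke ratio)

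Case A: true TIA ratio 2.0, ischemic stroke ratio 1.0. Case B: the reverse.

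| r | s | Case A | Case B |
|---|---|---|---|
| 0.25 | 0.25/1.25 = 20% | 0.80×2 + 0.20×1 = 1.80 | 0.80×1 + 0.20×2 = 1.20 |
| 1 | 1/2 = 50% | 0.50×2 + 0.50×1 = 1.50 | 0.50×1 + 0.50×2 = 1.50 |
| 2 | 2/3 = 67% | 0.33×2 + 0.67×1 = 1.33 | 0.33×1 + 0.67×2 = 1.67 |
| 4 | 4/5 = 80% | 0.20×2 + 0.80×1 = 1.20 | 0.20×1 + 0.80×2 = 1.80 |

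The share exceeds one half only when r is above 1.

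**The case against.** The strongest defence is that the plan may never report TIA on its own. The listed outcome is Stroke, the objective joins stroke and TIA in one item, and SAP 7.1 names only stroke for cumulative incidence. In a single first-event outcome, a code that appears on two lines counts nobody twice, and the dilution in the table does not arise. This stands, and it makes those harms conditional on separate reporting. It does not clear the plan: the sub-items are defined separately, nothing says they will only be pooled, and the confirmation question remains in the composite.

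On confirmation, the note follows the whole Stroke block and does not expressly exempt TIA. Because it names ischemic and hemorrhagic stroke and leaves TIA out, the reading that TIA needs no confirmation is the likelier one, but it is not certain. The supportable statement is that unconfirmed I63 claims could enter, not that they will.

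The line may also be a broad cerebral-ischemia set under a narrow label. The plan puts I690, I691 and I692 beside I60, I61 and I62, which suggests that I693 is the partner of I63. That is plausible, and it is a reason not to treat I693 as a stray hemorrhagic code. It would explain the overlap, but the label would still be wrong.

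A reader might infer that the TIA result by drug is mostly an ischemic stroke result. The documents do not support that. It needs more I63 than G459 entries, and no counts are given; at a ratio of 0.25 the share is only 20%.

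**Conclusion.** The definition is wrong as written. In all three places where the outcome is defined, every ischemic stroke is also a TIA, so the two sub-outcomes cannot be interpreted as separate results. That conclusion follows from the code lists and needs no assumption.

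The size is not known. Over assumed I63:G459 ratios of 0.25 to 4, between 20% and 80% of reported TIA cases would be ischemic stroke codes. A true TIA ratio of 2.0 would then appear as 1.80 down to 1.20. These figures apply only if TIA is reported separately, with ischemic stroke risk unchanged, and with I693 and dual-coded patients left aside.

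If only one stroke/TIA composite is analysed, double counting disappears. What remains is that I63 claims failing the hospitalization-and-imaging condition could enter through the TIA line.

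**What to change.** Make the change by a dated, justified SAP amendment covering SAP 5.2 and SAP Table 3, and bring Protocol Table 3 into line:

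1. Remove I63 from the TIA line, so that it counts only under ischemic stroke with the confirmation already stated.
2. Remove I693 from the TIA line, or justify it as part of a named cerebral-ischemia outcome.
3. State whether the hospitalization-and-imaging condition applies to TIA.

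Alternatively, if one cerebral-ischemia outcome is intended, relabel the line as a named composite (confirmed I63 or G459) that counts each patient once. Either way, say whether the stroke sub-items will be reported separately or only together.

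The cost is one code line in three places, a re-run of one outcome and a smaller TIA count. SAP section 1 records that the SAP was amended during data analysis, so the amendment should also say whether stroke or TIA results by drug had been seen when the list was changed.

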9.4. Data sources

The Korean HIRA claims data covers 97% of Korean population (about 50 million people) in NHI and 3% of Korean population in Medical Aid program. Patients in Medical Aid program are excluded from analysis because the estimated drug compliance may be different from those patients covered by NHI due to the fact that patients in Medical Aid program make no self-payment or very little payment for medical services (Ahn et al, 2011).

HIRA database from January 01, 2016 to December 31, 2019 will be used for the analysis. It contains the data of universal health insurance system in Korea, wherein patient demographic information, inpatient and outpatient service use, and pharmacy dispensing claims can be obtained.

The main limitation of HIRA data is lack of clinical lab data and other clinical markers since it is a data collected for claims for reimbursement purpose.

9.5. Study size

Determined based on the HIRA disease statistics, diagnosis code, inclusion and exclusion criteria, and study period. A previous study was conducted using the HIRA data from January 1, 2011 to December 31, 2015, during which 752,190 patients were identified to have been newly prescribed antidepressants with diagnosis of depressive disorder.

9.6. Data management

Ewha Womans University (EWU) team will submit the data request to the HIRA big data division. After HIRA prior consultation procedure and data release committee review and approval, the requested data will be uploaded only to the HIRA internal server which can be accessed from HIRA analysis room available in Wonju or remotely. Even if the data can be remotely accessed, copying and moving of data to personal computer is blocked and data provision will be suspended in the situation of screen capture, handwriting, or photography, all of which are subject to sanctions. EWU team hopes to analyze the data in remote access, however HIRA has a policy that does not allow remote access to industry-related users, and so the data provision method for this study cannot be predicted. Among the analyzed data, only summary data such as tables and graphs can be requested to send out to the research team. HIRA big data division checks the export requests for patient privacy protection and will email the summary file to EWU team.

Data protection is guaranteed by the HIRA data providing server which is disconnected from any outside access and only final anonymized form of tables and figures are allowed to be delivered to researcher computers. Before releasing these final output, HIRA Big Data Division checks for privacy protection again and makes approval of data export. Hence, there will be no violation of privacy of research subjects.

[figure not shown]
9.7. Data analysis

The proportions and drug utilization patterns comparisons of 11 study drugs will use all the patients satisfying inclusion and exclusion criteria (raw data). Adherence, persistence, discontinuation, recurrence, and adverse outcomes comparison of 11 study drugs will use both raw data and matched data where patients will be matched on demographic and clinical characteristics. All outcome variables will be summarized *descriptively* through the tabular and graphical display of mean values, medians, ranges and standard deviations of continuous variables of interest and frequency distributions of categorical variables. Safety outcomes of treatments will be estimated from time-to-event models. The 95% confidence intervals for the estimates will be calculated and $p < 0.05$ will be considered significant. All analyses will be carried out using SAS version 9.4 which is installed on HIRA server. Analysis and reporting will be compliant with Strengthening the Reporting of Observational Studies in Epidemiology (STROBE) recommendations.

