3 HYPOTHESES AND DECISION RULES

N/A

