7.2 STATISTICAL ANALYSES

7.2.1 Study Drug Analysis in Acute Phase

- To understand the top 11 antidepressants usage among the Korean patients with depression in acute treatment phase
- Primary analysis
- Endpoints:
 - Proportion of 11 antidepressants, by age (<20, 21-64, > 65), by gender, by age and gender
 - Choice of index drug
 - Initial doses used, average daily doses of each antidepressant
 - The average length of treatment with index medication before therapy change occurs (switching, combination, augmentation, discontinuation)
 - Adherence measured by medication possession ratio and persistence during first 90 days and 180 days of treatment period, respectively
- Population: patients who meet inclusion criteria and exclusion criteria in section 4.1 and classified by the index antidepressant out of 11 top antidepressants in the Korean market (Table 2)
- Significance on continuous variables will be tested by ANOVA (if equal variance condition satisfied) or the Kruskal-Wallis H test (otherwise). Provider specialty and other patient characteristics will be used to fit antidepressant choice by multivariate logistic regression analysis of each study drug choice.
- Covariates: antidepressant class covariates such as SSRIs, SNRIs, and other ADs will be used as grouping variables.
- Missing values will be dropped from the analysis
- The role of this analysis is to provide information on study antidepressants in the acute phase of drug therapy for Korean patients with depression.

PFIZER CONFIDENTIAL

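### Protocol 9.7 sets an unadjusted p<0.05 rule for comparing 11 drugs on nine primary adverse outcomes, while the SAP declares no hypotheses or decision rules and the contrasts are not named

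*Protocol*

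**What the plan says.** Protocol 9.7 states that the "adverse outcomes comparison of 11 study drugs will use both raw data and matched data", and lists adherence, persistence, discontinuation and recurrence in the same sentence. Safety outcomes are to be estimated from time-to-event models. It continues: "The 95% confidence intervals for the estimates will be calculated", and adds that "p < 0.05$ will be considered significant". The Protocol Abstract repeats this rule.

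The safety objective in Protocol section 8 is "Risk of adverse outcomes measurement between individual ADs that are well known to be treatment-related", with these examples: "hyponatremia, GI bleeding, fractures, falls, risk of intracranial hemorrhage, attempted suicide/self-harm, myocardial infarction, epilepsy/seizures, stroke/transient ischemic stroke". SAP 5.2 confirms that "Adverse outcomes are primary endpoints in this study" and defines the same nine categories by code. Table 3 of both documents also labels persistence, discontinuation, adherence and recurrence as primary.

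SAP section 3, titled "HYPOTHESES AND DECISION RULES", contains only N/A. SAP 7.1 nevertheless plans bivariate comparisons of outcome measures, with the t-test and chi-square test as examples. SAP 7.2.1 adds "Significance on continuous variables will be tested by ANOVA (if equal variance condition satisfied", with Kruskal-Wallis otherwise, and 7.2.2 to 7.2.5 repeat this. The primary objectives are framed as exploration, and Protocol 9.7 says that outcomes will be summarised descriptively.

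The available text of the two documents has no multiplicity adjustment, hierarchy of outcomes, reference drug or key comparison.

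**The concern.** A fixed threshold for calling results significant is a decision rule. Here it covers many comparisons on many primary outcomes, with nothing to limit how often chance alone crosses it. The SAP, the later document, says there are no decision rules, so the two documents disagree on whether the study makes significance claims at all.

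The stakes lie in the reporting. The sponsor's product, desvenlafaxine, is one of the 11 drugs, and Protocol section 12 plans journal and conference publication. Under the written rule, an isolated p<0.05 on suicide attempt, GI bleeding or myocardial infarction could be published as a significant difference between two antidepressants.

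**Working it through.** The plan gives no power, family-wise error rate or number of tests, so there is no stated figure to reproduce.

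**Inputs from the documents**
- Per-test level: 0.05 (Protocol 9.7), read as two-sided because it is paired with 95% intervals.
- Drugs: 11 (Protocol 9.7).
- Primary adverse-outcome categories: 9, counting stroke once (Protocol section 8; SAP 5.2).

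**Assumptions not in the documents**
- No drug truly differs from another on any outcome.
- Drug shares are either equal or unequal, from 30% for the most used to 2% for the least.
- Between-outcome correlation is 0, 0.6 or 0.9.

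**Step 1: number of tests.** The contrasts are not named, so three structures are taken.
- One overall 11-drug test per outcome: 9 tests.
- Each drug against one reference: 10 x 9 = 90 tests.
- All pairs: (11 x 10)/2 = 55 per outcome; 55 x 9 = 495 tests.

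**Step 2: expected false positives (tests x 0.05).** 9 x 0.05 = 0.45; 90 x 0.05 = 4.5; 495 x 0.05 = 24.75. Correlation does not change these.

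**Step 3: chance of at least one, with independent outcomes.**
- Overall tests: 1 - 0.95^9 = 0.370.
- Reference contrasts: the 10 contrasts within an outcome share the reference, so the per-outcome chance was simulated (20,000 runs, normal estimates). It is 0.287 at equal precision, and 1 - (1 - 0.287)^9 = 0.952. With the unequal shares it is 0.381, giving 1 - (1 - 0.381)^9 = 0.987 (0.986 when all nine outcomes were simulated together).
- All pairs: the per-outcome chance is that the studentized range of 11 equal groups exceeds 1.96 x √2, which is 0.677. Then 1 - (1 - 0.677)^9 = 0.99996.

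**Step 4: correlated outcomes.** Independence cannot hold exactly: SAP 5.2 uses I60-I62 and I690-I692 for both intracranial hemorrhage and hemorrhagic stroke. The same simulation with correlation added gives the following; ranges cover equal and unequal shares.

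| Structure | Tests | Expected false positives | Independent | Correlation 0.6 | Correlation 0.9 |
|---|---|---|---|---|---|
| Overall test per outcome | 9 | 0.45 | 37% | 25-26% | about 14% |
| Each drug vs one reference | 90 | 4.5 | 95-99% | 83-92% | 57-71% |
| All pairs | 495 | 24.75 | over 99.9% | about 99.4% | 91-92% |

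The table leaves out the other primary outcomes and the repetition in raw and matched data (Protocol 9.7), both of which add tests.

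**The case against.** The strongest objection is that all-pairs testing is an inference. Comparing individual drugs fits 55 pairs, ten contrasts against a reference, or one overall test. The only 11-group tests that the SAP names are overall tests, and SAP 7.2 also groups drugs into SSRIs, SNRIs and others. This stands. A reader might infer that false drug differences are almost certain, or that about 25 of them should be expected, or about 36 if the four other primary outcomes are added (55 x 13 = 715; 715 x 0.05 = 35.75). The documents do not support that as a general statement. It needs all-pairs testing, which neither document specifies, and a true absence of differences. The count of 715 also needs the threshold to cover every outcome, whereas the p<0.05 sentence directly follows the one on safety models and may refer to safety only.

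A reader might also take the ANOVA/Kruskal-Wallis sentence as evidence that the SAP tests the adverse outcomes for significance. It does not reach them: it is confined to continuous variables, and the adverse outcomes are coded events. By the same token, those overall tests offer no protection for the adverse outcomes. The threshold that does reach them is the one in Protocol 9.7, and SAP 7.1 allows two-group tests on outcome measures in general terms.

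Finally, an exploratory study need not control family-wise error. That is true, but it is an argument for dropping the significance rule, not for keeping it unadjusted.

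**Conclusion.** The concern holds in a conditional form. Protocol 9.7 states an unadjusted significance rule for a comparison of 11 drugs on nine primary adverse-outcome categories. SAP section 3 says that no decision rules apply, and neither document names the contrasts or controls multiplicity. With independent outcomes and no true differences, the chance of at least one false claim runs from about 37% to over 99.9%, depending on a choice that the plan leaves open. At a correlation of 0.9 the range is about 14% to 91-92%. Even the mildest case is nearly three times the nominal 5%.

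The correlations and drug shares are assumptions, testing is taken as two-sided, and every figure is under the global null. True differences or residual confounding could also produce p<0.05, and these figures do not describe that.

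**What to change.** Remove the p<0.05 rule from Protocol 9.7 and from the Abstract. Replace N/A in SAP section 3 with a statement that between-drug safety and compliance comparisons are exploratory. They would be reported as confounder-adjusted estimates with 95% confidence intervals, labelled as not adjusted for multiplicity, and no drug would be declared significantly different. Bring the significance wording in SAP section 7 into line. This costs wording only and fits the plan's own exploratory framing.

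If any pairwise claim is to be made, name the contrasts in advance, require an overall 11-drug test for that outcome, and follow it with Holm-adjusted p-values. The SAP should say that this controls error within each outcome and not across outcomes: nine independent outcomes each held at 5% still give 1 - 0.95^9 = 37%. This route costs more, because the SAP plans matching and weighting without defining an 11-way matched set, so the overall test in matched data would have to be specified first.

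The downside is that fewer results can be called significant. Holm over 55 pairs starts at 0.05/55 = 0.0009 and may miss signals for rare events, so the estimates and intervals should always be shown.
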